### 14.6.5. Evaluating AEs and SAEs

#### Assessment of Intensity

The investigator will make an assessment of intensity for each AE and SAE reported during the study and will assign it to one of the following categories:

- Mild: An event that is easily tolerated by the subject, causing minimal discomfort and not interfering with everyday activities.
- Moderate: An event that is sufficiently discomforting to interfere with normal everyday activities
- Severe: An event that prevents normal everyday activities. - an AE that is assessed as severe will not be confused with an SAE. Severity is a category utilized for rating the intensity of an event; and both AEs and SAEs can be assessed as severe.
- An event is defined as 'serious' when it meets at least one of the pre-defined outcomes as described in the definition of an SAE.

#### Assessment of Causality

- The investigator is obligated to assess the relationship between study treatment and the occurrence of each AE/SAE.
- A "reasonable possibility" is meant to convey that there are facts/evidence or arguments to suggest a causal relationship, rather than a relationship cannot be ruled out.
- The investigator will use clinical judgment to determine the relationship.
- Alternative causes, such as natural history of the underlying diseases, concomitant therapy, other risk factors, and the temporal relationship of the event to the study treatment will be considered and investigated.
- The investigator will also consult the Investigator Brochure (IB) and/or Product Information, for marketed products, in the determination of his/her assessment.
- For each AE/SAE the investigator **must** document in the medical notes that he/she has reviewed the AE/SAE and has provided an assessment of causality.
- There may be situations when an SAE has occurred and the investigator has minimal information to include in the initial report to GSK. However, **it is very important that the investigator always make an assessment of causality for every event prior to the initial transmission of the SAE data to GSK.**
- The investigator may change his/her opinion of causality in light of follow-up information, amending the SAE data collection tool accordingly.
- The causality assessment is one of the criteria used when determining regulatory reporting requirements.

**Follow-up of AEs and SAEs**

- The investigator is obligated to perform or arrange for the conduct of supplemental measurements and/or evaluations as may be indicated or as requested by GSK to elucidate as fully as possible the nature and/or causality of the AE or SAE.
- The investigator is obligated to assist. This may include additional laboratory tests or investigations, histopathological examinations or consultation with other health care professionals.
- If a subject dies during participation in the study or during a recognized follow-up period, the investigator will provide GSK with a copy of any post-mortem findings, including histopathology.
- New or updated information will be recorded in the originally completed CRF.
- The investigator will submit any updated SAE data to GSK within the designated reporting time frames.

**14.6.6. Reporting of SAEs to GSK****SAE reporting to GSK via electronic data collection tool**

- Primary mechanism for reporting SAEs to GSK will be the electronic data collection tool
- If the electronic system is unavailable for greater than 24 hours, the site will use the paper SAE data collection tool and e-mail it to the Medical Monitor
- Site will enter the serious adverse event data into the electronic system as soon as it becomes available.
- The investigator will be required to confirm review of the SAE causality by ticking the 'reviewed' box at the bottom of the eCRF page within 72 hours of submission of the SAE.
- After the study is completed at a given site, the electronic data collection tool (e.g., InForm system) will be taken off-line to prevent the entry of new data or changes to existing data
- If a site receives a report of a new SAE from a study subject or receives updated data on a previously reported SAE after the electronic data collection tool has been taken off-line, the site can report this information on a paper SAE form or to the Medical Monitor by telephone.
- Contacts for SAE receipt can be found at the beginning of this protocol on the Sponsor/Medical Monitor Contact Information page.

## 14.7. Appendix 7: Guidelines for Management of Toxicity

The following dose modification criteria should provide guidance for, but not act as a replacement for sound clinical judgment. The investigator should use clinical judgment to determine which drug may be contributing to the toxicity necessitating dose adjustment, and make the appropriate change for that drug. Dose modifications should be made after discussion with the GSK medical monitor.

### 14.7.1. Dose Adjustments for Toxicity

**Table 12 Dose Adjustment/Stopping Safety Criteria**

Toxicity	Dose Adjustment/Stopping Criteria	Management Guidelines
QTcF	If >30msec and < 60 msec change from baseline AND manual QTcF <500 (average of three ECGs over at least 15 minutes)	
 
Continue current dose of GSK2820151               
 
Supplement electrolytes, particularly potassium and magnesium, to recommended levels:                   
 
Maintain serum potassium > 4mol/L
 
Maintain serum magnesium levels >0.85 mmol/L
 
 
 
Discontinue any concomitant medications with potential for QTcF prolongation.
 
Consider 24 hour or longer telemetry monitoring if clinically indicated.
 
 
 

	If $\geq 60$ msec change from baseline occurs  OR  QTcF $\geq 500$  (average of three ECGs over at least 15 minutes)	
 
Discontinue GSK2820151 and notify the GSK Medical Monitor.               
 
Supplement electrolytes to recommended levels:                   
 
Maintain serum potassium > 4mol/L
 
Maintain serum magnesium levels >0.85 mmol/L
 
 
 
Rule out other potential etiologies for prolonged QTcF such as cardiac ischemia
 
Discontinue any concomitant medications with potential for QTcF prolongation.
 
Consider telemetry monitoring if clinically indicated.
 
 
 
This subject may consider restarting study treatment at a previous dose level if the following criteria for QTcF rechallenge are met:               
 
QTcF Rechallenge Procedures: Do not rechallenge with study treatment unless under the following conditions:                   
 
QTcF event reduced to <450 msec,
 
potassium and magnesium levels are within institutional normal range,
 
a favorable risk/benefit profile (in the medical judgement of the Investigator and the GSK Medical Monitor),
 
 
 
 
 

Toxicity	Dose Adjustment/Stopping Criteria	Management Guidelines
		
(4) approval within GSK medical governance:
 
 
a. agreement with SERM MD and PPL,
 
b. review with Chair or co-Chair of the GSK QT panel,
 
c. SERM VP and Clinical VP approval
 
d. Head Unit Physician approval
 
 
(5) Institutional IRB (or equivalent) approval, and
 
(6) The subject is re-consented regarding the possible increased risk of QTc prolongation.
 
 
• If approval for re-challenge is granted, the subject must be re-consented (with a separate informed consent specific to QTc prolongation)
 
• Discontinuation procedures: If the subject is withdrawn due to QTcF event, the subject should complete the following activities post-dose: 
 
(1) Evaluation by cardiologist.
 
(2) Weekly assessments for QTcF should be monitored weekly for two weeks, and then next assessment at 4 weeks post-dose.
 
           If QTcF results have not resolved to baseline by 4 weeks post-dose, then continue every 4-5 weeks until resolution         
 

Troponin	Troponin level >ULN	
 
• Contact the subject immediately for evaluation of symptoms and to obtain ECG. Repeat troponin within 24-48 hours or as soon as possible. 
 
• If the subject is asymptomatic and repeat value is within the normal range, the subject may continue GSK2820151 with close follow-up for symptoms, ECG monitoring and further troponin measurements as clinically indicated.
 
• If the repeat value remains > ULN AND the subject is asymptomatic, hold GSK2820151, refer to a cardiologist, and contact the GSK Medical Monitor. May consider restarting study treatment at a reduced dose or dose level pre-event based on discussion with GSK Medical Monitor.
 
• If the subject is symptomatic (symptoms consistent with acute coronary syndrome) OR the troponin level is at or above the threshold for myocardial infarction (MI) according to local lab parameters, discontinue GSK2820151 permanently and refer the subject immediately to a cardiologist or emergency medical facility for appropriate medical care.
 
 
 

Toxicity	Dose Adjustment/Stopping Criteria	Management Guidelines
LVEF	Ejection fraction below the institution's lower limit of normal (LLN)  AND  An asymptomatic, absolute decrease of >10% in LVEF compared to baseline	Withhold GSK2820151 and repeat evaluation of LVEF within 2 weeks  If LVEF recovers (defined as $\geq$ LLN and absolute decrease $\leq$ 10% compared to baseline) at any time during the next 4 weeks, after consultation and approval of the GSK medical monitor, the subject may be restarted on investigational drug(s) at a reduced dose. Monitoring to be performed at 2 and 4 weeks after restarting investigational drug(s) and then per protocol specifications.  If LVEF does not recover within 4 weeks, permanently discontinue investigational drug(s). Evaluation by a cardiologist will be conducted. Ejection fraction should continue to be monitored at 2 weeks, 4 weeks and every 4 weeks until 16 weeks or resolution, whichever is longer.
	Grade 3 or 4	Permanently discontinue GSK2820151. Evaluation by a cardiologist will be conducted. Ejection fraction should be monitored at 2 weeks, 4 weeks and then every 4 weeks until 16 weeks or resolution, whichever is longer.
Liver		Refer to procedures outlined in Appendix 3: Liver Safety Required Actions and Follow up Assessments
Hypo- and Hyperglycemia  Note: for management purposes, refer to mild, moderate and severe intensity criteria; however for CRF reporting use NCI-CTCAE version v4.03 Grade 1-5	Fasting blood glucose >150 mg/dL to 250 mg/dL (Mild hyperglycemia)	
 
Monitor fasting and preprandial glucose.
 
If persistent over 2 repeats over 3-4 weeks, consult Diabetologist and consider starting metformin
 

	Any blood glucose >250 mg/dL (Moderate to Severe hyperglycemia)	
 
Withhold GSK2820151 and instruct subject to notify investigator immediately. 
 
Monitor for ketoacidosis as clinically indicated.
 
If subject has evidence of ketoacidosis, initiate prompt therapy. Antihyperglycemic therapy with insulin is preferred. Consult Diabetologist/Endocrinologist . Careful monitoring should be performed to control for rebound hypoglycemia as effect of investigational product(s) resolve.
 
 
 
May consider restarting GSK2820151 at a reduced dose or dose level pre-event based on discussion with GSK Medical monitor.
 

Toxicity	Dose Adjustment/Stopping Criteria	Management Guidelines
	Fasting blood glucose <70 mg/dL (Moderate to Severe hypoglycemia)	
Withhold GSK2820151
 
Provide sugar containing liquids and monitor blood sugar closely. Check for insulin and c-peptide levels. After blood sugar normalizes, may restart study treatment one dose level lower if the hypoglycemia cannot be attributed to any other cause, and fasting blood sugar will be monitored on a daily basis until the blood glucose level is stabilized.

Diarrhea	Grade 1	
 
Initiate supportive care including loperamide.
 

	Grade 2	
 
Initiate supportive care including loperamide.
 
Consider temporary discontinuation of GSK2820151 and discuss with GSK Medical Monitor.
 

	Grade 3	
 
Above plus consider intravenous (IV) hydration, hospital admission and prophylactic antibiotics as appropriate.
 
Withhold GSK2820151 until diarrhea has resolved to <math>\leq</math>Grade 1, continue diarrheal prophylaxis. If diarrhea recovers to <math>\leq</math> Grade 1, discuss with medical monitor; consider resuming treatment at the same or lower dose based on clinical judgement.
 

	Grade 4	
 
Above plus consider intravenous (IV) hydration, hospital admission and prophylactic antibiotics as appropriate.
 
Discontinue GSK2820151 permanently
 

Mucositis	Grade 1 or 2	
 
Encourage oral hygiene. Offer topical supportive anesthetics. Encourage adequate hydration.
 

	Grade 3 or 4	
 
Above, plus systemic opiate administration as needed. 
 
Consider IV hydration and hospital admission as appropriate.
 
For mucositis <math>\geq</math> Grade 3, withhold GSK2820151 until mucositis is <math>\leq</math> Grade 1 and resume the same dose of GSK2820151. If mucositis <math>\geq</math> Grade 3 recurs, withhold GSK2820151 until mucositis is <math>\leq</math> Grade 1, then reduce GSK2820151 one dose level. If mucositis <math>\geq</math> Grade 3 recurs a third time at reduced dose, discontinue GSK2820151 permanently.
 
 
 

Pneumonitis	Grade 1	
 
Consider evaluation by pulmonologist. 
 
Consider room air O2 saturation at rest via pulse oximetry reading (X 2, 5 mins apart). If any decline is observed in O2 saturation,
 
 
 

Toxicity	Dose Adjustment/Stopping Criteria	Management Guidelines
		
withhold study drug, repeat chest x-ray to determine if progression of pneumonitis has occurred and consult pulmonologist.
 
 
Obtain high-resolution computed tomography (CT) scan of the chest if possible.
 

	Grade 2	
 
, then reduce dose by at least 25%.
 
Must be evaluated by pulmonologist. 
 
Consider pulmonary function tests including: spirometry, Diffusing Capacity of the Lung for Carbon Monoxide (DLCO), and weekly room air O2 saturation at rest via pulse oximetry reading (X 2, 5 mins apart). Repeat evaluations every 8-12 weeks until return to baseline.
 
Obtain high-resolution chest CT if possible.
 
Consider a bronchoscopy with biopsy and/or bronchoalveolar lavage. (BAL).
 
Treat only if symptomatic. Consider corticosteroids if symptoms are troublesome and infective origin is ruled out. Taper as medically indicated.
 
 
 
Withhold GSK2820151 until recovery to ≤ Grade 1, then reduce dose by at least 25%. Discontinue GSK2820151 if no recovery to ≤Grade 1 within 4 weeks.
 

	Grade 3 or 4	
 
Discontinue GSK2820151 and refer for evaluation by pulmonologist 
 
Required pulmonary function tests including: spirometry, DLCO, and room air O2 saturation at rest via pulse oximetry reading (X 2, 5 mins apart). Repeat evaluations at least every 8 weeks until return to baseline.
 
Obtain high-resolution chest CT if possible.
 
Bronchoscopy with biopsy and/or BAL is recommended.
 
Consider corticosteroids if infective origin is ruled out. Taper as medically indicated.
 
 
 
Rechallenge Guidelines 
 
Grade 3: Withhold GSK2820151 until recovery to < Grade 1. Discontinue GSK2820151 if no recovery to < Grade 1 within 4 weeks. May consider restarting GSK2820151 at a reduced dose after discussion with GSK Medical Monitor if there is clinical benefit.
 
Grade 4: Rechallenge with GSK2820151 is not permitted
 
 
 

Toxicity	Dose Adjustment/Stopping Criteria	Management Guidelines
Fever	Grade 1	
 
Continue current dose of GSK2820151 and monitor for change in severity.
 

	Grade 2	
 
Temporarily discontinue GSK2820151 and monitor for change in severity. 
 
Assess or inquire if the subject is experiencing in combination with fever: swelling, redness, extreme fatigue or nausea. Assess vital signs.
 
Collect cytokine blood samples as outlined in the Laboratory Manual. Collect blood culture and investigate viral infections as applicable
 
 
 
Consider restarting study treatment at a reduced dose or dose level pre-event based on discussion with GSK Medical monitor.
 

	Grade 3 or 4	
 
Temporarily discontinue study medication and monitor for change in severity. 
 
Assess or inquire if the subject is experiencing in combination with fever: swelling, redness, extreme fatigue or nausea.
 
Collect cytokine blood samples as outlined in the Laboratory Manual. Collect blood culture and investigate viral infections as applicable.
 
 
 
Consider restarting study treatment at a reduced dose or dose level pre-event based on discussion with GSK Medical Monitor
 

Thrombocytopenia	Grade 1 (platelets <LLN to $\geq 75,000/\text{mm}^3$ ) or Grade 2 (platelets <75,000 to $\geq 50,000/\text{mm}^3$ )	
 
Continue dosing at same dose level with weekly or more frequent monitoring as necessary
 

	Grade 3 (platelets <50,000 to $\geq 25,000/\text{mm}^3$ )	
 
Withhold GSK2820151 and check aPTT, PT, and INR. Monitor CBC and coagulation studies twice a week until normal, or increase monitoring frequency if clinically indicated.
 
Withhold GSK2820151 until thrombocytopenia has resolved to <math>\leq</math> Grade 2 AND aPTT, PT, and INR are all <math>\leq</math> ULN. Drug may then be restarted at a lower dose level, after discussion with the medical monitor.
 
If safety lab abnormalities recur following rechallenge, drug may be discontinued permanently or restarted at further lower dose level, after discussion with the medical monitor. If safety lab abnormalities recur to the same level following a second rechallenge, drug
 

Toxicity	Dose Adjustment/Stopping Criteria	Management Guidelines
		will be discontinued permanently.
	Grade 4 ( platelets $\leq$ 25,000) or any moderate to severe bleeding accompanied by drug related thrombocytopenia	
Withhold GSK2820151 and check aPTT, PT, and INR. Monitor CBC and coagulation studies twice a week until normal, or increase monitoring frequency if clinically indicated.
 
Withhold GSK2820151 until thrombocytopenia has resolved to <math>\leq</math> Grade 2 AND aPTT, PT, and INR are all <math>\leq</math> ULN. Drug may then be restarted at a lower dose level, after discussion with the medical monitor.
 
If safety lab abnormalities recur following rechallenge, drug may be discontinued permanently.
 
If platelet count does not recover to <math>\geq</math>25,000/mm^3 (Grade 3) within 7 days and <math>\geq</math>50,000/mm^3 (Grade 2) within 14 days, GSK2820151 should be permanently discontinued.
 
Any subject requiring transfusion support, GSK2820151 should be permanently discontinued.
 
 
•
 

All Other Toxicity*	1	
 
• Continue dosing with no change
 

	2	
 
• Continue dosing with no change
 
 
OR
 
 
• Withhold GSK2820151 for up to 1 week for toxicity to be <math><</math> Grade 2, then continue at the same dose (dose reduction is required if the grade 2 toxicity is considered a DLT)
 

	3	
 
• 1st episode: Withhold dose for one week intervals until <math>\leq</math> drug-related Grade 2, then restart with no change.
 
• 2nd episode: Utilize an alternative, less frequent schedule or reduce by one dose level.
 
• If no recovery to <math>\leq</math>Grade 1* after a 21 day delay, patient should go off protocol therapy.
 

	4	
 
• Discontinue GSK2820151
 
• In rare situations, based on discussion and written agreement between GSK medical monitor and investigator, if the subject is receiving benefit then the episode may be managed as per Grade 3 toxicity.
 

\*Note: Exceptions to  $\leq$  drug-related Grade 1 requirement may be made for certain AEs as defined in Section 4.2.5.

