5. Evidence of severe or uncontrolled systemic diseases (e.g., unstable or uncompensated respiratory, hepatic, renal, cardiac disease, or clinically significant bleeding episodes). Any serious and/or unstable pre-existing medical (aside from malignancy), psychiatric disorder, or other conditions that could interfere with subject's safety, obtaining informed consent or compliance to the study procedures, in the opinion of the Investigator.
6. Symptomatic or untreated leptomeningeal or brain metastases or spinal cord compression.

**NOTE:** Subjects previously treated for these conditions that have had stable central nervous system (CNS) disease (verified with consecutive imaging studies) for >1months, are asymptomatic and off corticosteroids, or are on stable dose of corticosteroids for at least 1 month prior to study Day 1 are permitted. Stability of brain metastases must be confirmed with imaging. Subject treated with gamma knife therapy can be enrolled 2 weeks post-procedure as long as there are no post-

procedure complications/stable. In addition, subjects treated or currently taking enzyme-inducing anticonvulsant (EIA) are allowed on study.

7. Cardiac abnormalities as evidenced by any of the following:
  - History of or current “untreated” clinically significant uncontrolled arrhythmias.
  - Clinically significant conduction abnormalities or arrhythmias
  - Presence of cardiac pacemaker
  - History or evidence of current  $\geq$ Class II congestive heart failure as defined by New York Heart Association (NYHA).
  - History of acute coronary syndromes (including unstable angina and myocardial infarction), coronary angioplasty, or stenting within the past 3 months. Subjects with a history of stent placement requiring ongoing antithrombotic therapy (e.g., clopidogrel, prasugrel) will not be permitted to enroll.
8. Following electrocardiogram (ECG) finding:
  - Baseline corrected QT (Fridericia’s formula) interval (QTcF)  $\geq$ 450 msec

**NOTE:** Any clinically significant ECG assessments should be reviewed by the site cardiologist prior to study entry.
9. Any of the following liver findings:
  - ALT  $>$ 2.5xULN
  - ALT  $>$  5xULN with liver metastases/tumor infiltration
  - Bilirubin  $>$ 1.5xULN (isolated bilirubin  $>$ 1.5xULN is acceptable if bilirubin is fractionated and direct bilirubin  $<$ 35%).

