#### 5.4.2. QTc Stopping Criteria

If a subject meets the corrected QT (QTc) interval duration criteria below, study treatment(s) will be withheld.

- QTcF interval  $\geq$  500 msec OR interval increase from baseline  $\geq$  60 msec: GSK2820151 will be discontinued unless the benefits of therapy outweigh the risk of rechallenge in the opinion of the investigator, the GSK Medical Monitor, as well as the GSK medical governance. In this situation, rechallenge may be permitted (see [Appendix 7](#) for rechallenge guidelines).

**NOTE:** QT interval duration criteria should be based on the average QTc value of triplicate electrocardiograms (ECGs) to include manual over-read. For example, if an ECG demonstrates a prolonged QT interval, obtain 2 additional ECGs over a brief period (e.g., within approximately 10 minutes of the abnormal ECG, if possible, and approximately 10 minutes apart from each other), and then use the averaged QTc values of the 3 ECGs to determine whether the subjects should have study treatment discontinued.

The QTc is the QT interval corrected for heart rate according to Fridericia's formula (QTcF).

- For eligibility and withdrawal, QTcF will be used for all subjects.
- For purposes of data analysis, QTcF will be used.

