#### **5.4.4. Valvular Toxicity Stopping Criteria**

Subjects who have a new asymptomatic, moderate regurgitation or stenosis by echocardiogram (ECHO) (Grade 2 mitral/tricuspid/aortic valvular toxicity per NCI-CTCAE v4.03) should temporarily discontinue GSK2820151 and have a repeat evaluation by ECHO within 1 week. ECHO should be repeated every 1 to 2 weeks for 4 weeks or until valve recovery to baseline.

- If the valve recovers to baseline any time during the next 4 weeks after consultation with and approval from the GSK Medical Monitor, the subject may be restarted on GSK2820151 at a reduced dose(s). For such subjects, monitoring of the valve via ECHO will then be performed 2 and 4 weeks after rechallenge, and every 4 weeks thereafter for 16 weeks and then per protocol.
- If repeat ECHO does not reveal valve recovery to baseline within 4 weeks, then the subject should permanently discontinue GSK2820151. The valve should continue to be monitored via ECHO every 4 weeks for 16 weeks or until resolution.

Subjects with a Grade 3 or 4 (symptomatic, severe regurgitation/stenosis by imaging with symptoms controlled by medical intervention) valvular toxicity must discontinue GSK2820151. Valvular toxicity should continue to be monitored every 4 weeks for 16 weeks or until resolution. If recovery occurs (return to baseline via imaging AND symptom resolution) within 4 weeks, the subject may restart GSK2820151 at a reduced dose after consultation with and approval from the GSK Medical Monitor.

ECHO must be performed at baseline and at the final study visit. Copies of all ECHO(s) and cardiology consultations performed on subjects who experience valvular toxicity will be required by GSK for review. Instructions for submitting qualifying ECHOs are provided in the Study Reference Manual (SRM).

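### QTcF rechallenge is judged on an absolute value only, so a subject with a baseline below 390 msec can pass the recovery test while the 60 msec stopping trigger is still met

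*Protocol*

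**What the plan says.** The QTcF row of Table 12 has two stopping triggers joined by OR: a rise of 60 msec or more ("msec change from baseline occurs") and an averaged QTcF of 500 msec or more. Either one leads to discontinuation. Restart at a previous dose level may then be considered, subject to "QTcF Rechallenge Procedures: Do not rechallenge with study treatment unless under the following conditions". There are six conditions:

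1. "QTcF event reduced to" below 450 msec;
2. normal potassium and magnesium;
3. a favourable risk/benefit judgement by the investigator and Medical Monitor;
4. sponsor governance approval, including review with the QT panel chair or co-chair;
5. IRB approval;
6. "The subject is re-consented regarding the possible increased risk of QTc prolongation".

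Protocol Section 5.4.2 repeats the two triggers ("If a subject meets the corrected QT (QTc) interval duration criteria below, study treatment(s) will be withheld"), refers to Appendix 7 for rechallenge, and gives no recovery value of its own. Return of QTcF to baseline appears in Table 12 only in the follow-up schedule for subjects withdrawn for a QTcF event. Exclusion criterion 8 in Section 5.2 excludes a baseline QTcF of 450 msec or more and sets no lower limit.

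**The concern.** One of the two stopping triggers is relative to the subject's own baseline, but the only QTcF recovery test is absolute. A subject with a low baseline can be stopped for a large rise, still show a rise of stopping size, and satisfy condition 1. Conditions 2 to 6 contain no QTcF value, so nothing else in the list supplies the missing test.

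Other cardiac rules in the same protocol do tie recovery to baseline. After an asymptomatic LVEF fall of more than 10% (absolute), Table 12 requires both LVEF at or above the institutional lower limit and a fall from baseline of 10% or less. For Grade 2 valve toxicity, Section 5.4.4 says "If the valve recovers to baseline any time during the next 4 weeks after consultation with and approval from the GSK Medical Monitor", restart at a reduced dose is possible.

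At stake is re-exposure of a subject whose QTcF is still prolonged by the protocol's own definition. The Section 4.6.1 risk table lists QT prolongation for this drug: up to 34 msec in dogs, lasting up to 48 hours after a single dose. It calls a direct hERG effect unlikely, and the mechanism and the torsades risk unclear.

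**Working it through.** The plan states no figure to reproduce; the check is a comparison of thresholds.

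**Inputs**
- Stop: Q − B ≥ 60, or Q ≥ 500 (Table 12; Section 5.4.2), where B is baseline and Q the current averaged QTcF, in msec.
- Rechallenge condition 1: Q < 450 (Table 12).
- Eligible baseline: B < 450, no lower limit (Section 5.2, criterion 8).

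**When both can hold.** The relative trigger needs Q ≥ B + 60 and condition 1 needs Q < 450. Some Q satisfies both if and only if B + 60 < 450, that is, B < 390. The 500 msec trigger cannot overlap with Q < 450, so the gap concerns the relative trigger alone.

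**Size, in whole msec.** The highest Q meeting condition 1 is 449, so the largest residual rise is 449 − B. If a rise below 60 were also required, the highest permitted Q would be the smaller of 449 and B + 59.

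| Baseline B | 60 msec trigger fires at B + 60 | Rise at Q = 449 | Highest Q with added clause | Extra fall required |
|---|---|---|---|---|
| 360 | 420 | 89 | 419 | 30 |
| 370 | 430 | 79 | 429 | 20 |
| 380 | 440 | 69 | 439 | 10 |
| 389 | 449 | 60 | 448 | 1 |
| 390 | 450 | 59 | 449 | 0 |
| 400 | 460 | 49 | 449 | 0 |

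At baselines of 389 and below, the trigger fires at a value that is already under 450.

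**Does the word *reduced* close the gap?** It implies some fall from the event value but sets no amount.
- Baseline 380, event 452 (+72), later 449 (+69): a 3 msec fall satisfies condition 1, and the rise is still above 60.
- Baseline 370, event 445 (+75), later 435 (+65): same result.

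In both cases the subject still meets the Section 5.4.2 criterion for withholding treatment.

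**The case against.** The strongest reply is that condition 1 is a necessary condition and gives no entitlement to restart. Section 5.4.2 still applies to a subject at +69 msec, and restart needs an explicit benefit-over-risk decision. The approval route is heavy: governance sign-off at several levels, QT-panel review, IRB approval and a separate consent, with restart at a previous dose level. The introduction to Appendix 7 calls its criteria guidance that does not replace clinical judgement. The 450 msec figure also has a rationale, since it returns the subject to the range allowed at entry.

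The comparators are not uniform either. After symptomatic Grade 3 or 4 LV dysfunction, Section 5.4.3 allows restart on an absolute LVEF limit plus symptom resolution (Table 12 permanently discontinues these subjects). Appendix 4 gives no numeric recovery threshold for rechallenge after liver injury possibly related to the drug.

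Finally, the scenario is narrow. It needs a low baseline and a large rise that persists off drug through several approvals, although the predicted half-life is about 5 hours. Section 8.3.6.1 also requires safety ECG review before each new week's dosing in the first cycle. The SAP Introduction reports that only five subjects enrolled.

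Much of this stands as to likelihood: such a rechallenge would probably be refused. It does not remove the gap. Section 5.4.2 hands rechallenge to Appendix 7 without adding a recovery value. The weekly ECG review looks for significant abnormalities without naming a threshold, and only in the first cycle. Less demanding rules elsewhere do not make the QTcF stop and recovery rules agree. Having chosen to include a numeric test, the plan should use one that cannot be passed while the stopping condition persists.

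**Conclusion.** The concern holds. Of the two QTcF stopping triggers, the relative one has no matching recovery criterion. For every baseline below 390 msec the written test can be met at a rise of 60 msec or more, and the possible residual rise grows by 1 msec for each msec that baseline is lower. At 390 msec and above the rules are consistent.

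This rests on the thresholds as written in the current protocol and on the absence of a lower limit for baseline QTcF. The residual rises tabulated are the largest possible at each baseline, not expected values. The documents give neither a distribution of baseline QTcF nor a rate of QTcF stops, so no share of subjects is estimated. The practical likelihood is low because of the approval steps, but this is a cardiac safety rule in a first-in-human study and the correction is cheap, so it should be made.

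**What to change.** Reword rechallenge condition 1 in Table 12 to require *QTcF reduced to below 450 msec and change from baseline below 60 msec*. Below 60 msec (with QTcF under 500) is where the same table lets dosing continue, so the stop and restart rules would then agree. A stricter limit would be a matter of preference and is not needed to close the gap.

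The cost is one clause. Baseline and triplicate QTcF are already collected, so no new assessment is needed. Nothing changes for baselines of 390 to 449 msec. Below that, QTcF must fall a further 390 − B msec before rechallenge can be considered, so some rechallenges will wait longer.
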